## 6.2. Planned Dose Adjustments

No planned dose adjustment is allowed.

## 6.3. Blinding

This will be a double-blind study and both subject and study staff will remain blinded to treatment. The following will apply:

- The investigator or treating physician may unblind a subject's treatment assignment **only in the case of an emergency** OR in the event of a serious medical condition when knowledge of the study treatment is essential for the appropriate clinical management or welfare of the subject as judged by the investigator.
- Investigators have direct access to the subject's individual study treatment via the IWRS system but this information should only be acquired in the case of an emergency.
- It is preferred (but not required) that the investigator first contacts the Medical Monitor or appropriate GSK study personnel to discuss options **before** unblinding the subject's treatment assignment.
- If GSK personnel are not contacted before the unblinding, the investigator must notify GSK as soon as possible after unblinding, but without revealing the treatment assignment of the unblinded subject, unless that information is important for the safety of subjects currently in the study.
- The date and reason for the unblinding must be fully documented in the CRF.
- GSK's Global Clinical Safety and Pharmacovigilance (GCSP) staff may unblind the treatment assignment for any subject with an SAE. If the SAE requires that an expedited regulatory report be sent to one or more regulatory agencies, a copy of

the report, identifying the subject's treatment assignment, may be sent to investigators in accordance with local regulations and/or GSK policy.

- The independent methHb assessor at the site and the independent data manager at GSK will have access to the methHb data which could potentially unblind them to the 8-aminoquinoline treatment arms. However, these data will be handled and stored securely and these personnel will not have access to other data for the study.

#### **6.4. Packaging and Labeling**

The following study treatment will be provided for each subject:

- Open label DHA-PQP tablets sufficient for 3 days dosing (3 or 4 tablets per day according to weight –refer to Section 6)
- One bottle containing 2 tafenoquine tablets (150mg per tablet) or 2 matched placebo tablets
- One bottle containing 16 overencapsulated primaquine tablets (15mg per overencapsulated tablet) or 16 matched placebo capsules (i.e. sufficient for 14 days dosing and 2 spare capsules)

The contents of the label will be in accordance with all applicable regulatory requirements.

#### **6.5. Preparation/Handling/Storage/Accountability**

No special preparation of study treatment is required.

- Only subjects enrolled in the study may receive study treatment and only authorized site staff may supply or administer study treatment. All study treatments must be stored in a secure environmentally controlled and monitored (manual or automated) area in accordance with the labelled storage conditions with access limited to the investigator and authorized site staff.
- The investigator, institution, or the head of the medical institution (where applicable) is responsible for study treatment accountability, reconciliation, and record maintenance (i.e. receipt, reconciliation and final disposition records).
- Further guidance and information for final disposition of unused study treatment are provided in the SRM.
- Under normal conditions of handling and administration, study treatment is not expected to pose significant safety risks to site staff.
- A Material Safety Data Sheet (MSDS)/equivalent document describing occupational hazards and recommended handling precautions either will be provided to the investigator, where this is required by local laws, or is available upon request from GSK.

## **6.6. Compliance with Study Treatment Administration**

Subjects will receive all doses of study treatment at the site directly from the investigator or designee, under medical supervision. The date and time of each dose administered in the clinic will be recorded in the source documents. The dose of study treatment and study subject identification will be confirmed at the time of dosing by a member of the study site staff other than the person administering the study treatment.

## **6.7. Study Treatment Overdose**

An overdose for this study will be considered as any dose of study treatment that is more than the planned dose for each dosing occasion.

### **DHA-PQP**

No specific antidote for DHA-PQP has been identified. In the event that overdose or toxicity does occur, individuals should stop the medication. Symptomatic and supportive therapy should be given as appropriate, including ECG monitoring because of the possibility of QTc interval prolongation.

### **Tafenoquine**

No specific antidote for tafenoquine has been identified. In the event that overdose or toxicity occurs, individuals should be managed with appropriate supportive measures and clinical judgement. Immediate induction of emesis and/or gastric lavage is not recommended. Hemodialysis is unlikely to be clinically useful as tafenoquine is highly protein-bound.

Methemoglobinemia has been observed in clinical trials at therapeutic doses of tafenoquine; clinically significant levels could possibly be encountered in overdose. Signs and symptoms of methemoglobinemia include (but are not limited to) blue discoloration of the skin and lips, and shortness of breath.

## Primaquine

No specific antidote for PQ has been identified. In the event that overdose or oxicity occurs, individuals should stop the medication and be managed with appropriate supportive measures and clinical judgement. Immediate induction of emesis and/or gastric lavage is not recommended.

Symptoms of PQ overdose include abdominal cramps, vomiting, burning, epigastric pain, central nervous system and cardiovascular disturbances, cyanosis, methemoglobinemia, moderate leukocytosis or leukopenia and anemia.

In the event of an overdose of any study treatment the investigator or treating physician should:

1. Contact the Medical Monitor immediately
2. Closely monitor the subject for adverse events (AEs)/serious adverse events (SAEs) and laboratory abnormalities until resolution.
3. Obtain a plasma sample for pharmacokinetic (PK) analysis if requested by the Medical Monitor (determined on a case-by-case basis)
4. Document the quantity of the excess dose as well as the duration of the overdosing in the eCRF.

Decisions regarding dose interruptions or modifications will be made by the investigator in consultation with the Medical Monitor based on the clinical evaluation of the subject.

## 6.8. Treatment after the End of the Study

All subjects who complete the Day 180 visit and have not had a recurrence of *P. vivax* malaria, will be treated with open label PQ (0.5mg/kg daily for 14 days) to minimize the likelihood of *P. vivax* relapses occurring after the end of the study. This medication will be sourced locally and will be taken together with food. Subjects who receive open label PQ at the end of the study will be required to return to the clinic for a safety follow up visit, 15 days later. PQ administration at the end of the study will be recorded in the eCRF.

The investigator is responsible for ensuring that consideration has been given to the post-study care of the subject's medical condition, whether or not GSK is providing specific post-study treatment.

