- Hemoglobin decreases of  $\geq 30\%$  or  $>3\text{g/dL}$  from baseline or, a drop in absolute hemoglobin to  $<7.0\text{g/dL}$ , in the first 15 days will be reported as a protocol-defined SAE even if asymptomatic and not requiring medical intervention. Blinded study treatment will be stopped immediately if a subject meets the protocol-defined SAE criteria for Hb drop together with clinical or laboratory evidence of hemolysis (refer to Section 5.4.2 and Section 7.5.1.1).

- Exploratory CYP2D6 genotype analyses will be undertaken to test the hypothesis that null and/or intermediate metabolizers of 8-aminoquinoline drugs are more at risk of *P. vivax* relapse with PQ but not TQ [Bennett, 2013].
- The primary analysis population will be the Intent To Treat (ITT) population
- A subject is considered to have completed the double-blind study if they are randomized to blinded study treatment and complete the Day 180 visit.
- Subjects who have not relapsed prior to the Day 180 visit will be given open label PQ 0.5mg/kg daily for 14 days to minimize the likelihood of *P. vivax* recurrence after the end of the study. These subjects will return for a final safety follow up visit 15 days later.
- If it is not possible to completely recruit the study from a single battalion but at least 120 subjects have been randomized, a blinded review of the relapse data will be conducted, with the intention to stop enrolment early if this review predicts that the combined relapse rate will be  $\geq 26.7\%$  at the end of the follow up period (based on sample size assumptions). Kaplan-Meier estimates will be made of the overall six month relapse rate, using all of the data available at that time. If this relapse criterion is met, enrolment will stop and the study will be analyzed once all the existing subjects have completed the 6 months follow up. If the blinded review predicts that the relapse rate will be  $< 26.7\%$ , further subjects will be recruited from a second battalion, up to a maximum of 150 subjects in total (See Section 9.2.3).
- The study design schematic is provided in Figure 1.

Figure 1 200894 Study Design Schematic

Open label DHA-PQP 3 or 4 tablets per day (according to weight) on Days 1-3 plus blinded study treatment as follows:

- 1) Tafenoquine 300 mg single dose on Day 1 and placebo for primaquine on Day 1-14\*
- 2) Primaquine 15mg on Days 1-14 and placebo for tafenoquine on Day 1\*

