Justification for DHA-PQP alone arm (relapse control arm): All subjects will receive the standard 3 day course of DHA-PQP which is expected to clear the initial blood stage infection. The inclusion of the DHA-PQP alone arm provides a relapse prevention placebo-control arm for the primary comparison of TQ versus no anti-hypnozoite treatment to confirm and quantify TQ efficacy in preventing relapse. Therefore, no subject will be left untreated for their acute malarial infection. All subjects will be under close observation and will be asked to report to the clinic at any time if they feel unwell or develop a fever. The research team aims to treat recurrent acute malaria at the earliest possible stage thereby ensuring subject safety and minimizing discomfort as a consequence of having malaria. Subjects who develop a recurrent parasitemia (symptomatic or asymptomatic) will receive immediate rescue treatment according to local treatment guidelines (see Section 6.9.1.2). On-site clinic facilities will be available 24 hours, 7 days a week to ensure the prompt management of any subject who relapses during the study. To ensure that all subjects do receive anti-hypnozoite treatment, subjects who have not relapsed by Day 180 will be dosed with PQ 0.5mg/kg daily for 14 days to minimize the likelihood of *P.vivax* recurrences after the end of the study.

The DHA-PQP alone arm is considered crucial to the study design to evaluate the true efficacy of TQ in preventing relapse. The underlying relapse rate following a course of

DHA-PQP cannot be assumed from historical data due to the natural variation in both infection rates and relapse rates among infected subjects. Therefore, it is essential to measure the relapse rate following treatment with DHA-PQP alone in the same setting and time as the study treatment arms.

Although local treatment guidelines recommend an ACT plus PQ for radical cure of *P. vivax*, in real life, PQ is used infrequently because of concerns about its potential to cause red cell hemolysis in G6PD deficient subjects and facilities for assessing G6PD status are lacking. Additionally, compliance with unsupervised PQ is low.

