#### **4.6.2. Benefit Assessment**

In the absence of radical cure treatment, a percentage of subjects with *P. vivax* malaria will relapse due to the liver being infected with hypnozoites (the dormant form of the parasite). *P. vivax* can cause a debilitating fever as it preferentially invades reticulocytes as well as causing bystander hemolysis, which can also lead to the development of anemia. Repeated relapses are similarly debilitating and may result in further episodes of fever, weight loss, malnutrition and high output heart failure. Other consequences are loss of work, time at school missed and hospitalization due to vomiting, dehydration and anemia (resulting in the need for transfusion).

Subjects may benefit from participating in this study since they will be closely followed for 6 months, thus ensuring that any malaria recurrences will be appropriately treated and concurrent conditions managed. Any subject who has not relapsed by the 6 month timepoint will be treated with open label PQ for 14 days, to ensure that all participants receive anti-hypnozoite medication as part of the study. In the future, patients with *P. vivax* malaria may benefit from TQ since it can be administered as a single oral dose (due to its long half life) and is therefore a more convenient treatment regimen compared with the standard 14 day regimen of PQ, with the potential to improve patient compliance. Improved compliance should lead to improved clinical outcomes for patients with *P. vivax* malaria by further reducing relapse rates.

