### **Premature Withdrawal of Study Treatment**

If a subject prematurely discontinues from study treatment for any reason or reaches the primary endpoint of relapse, they should continue to attend study visits to Day 180. The reason for withdrawal from treatment should be recorded in the electronic case record form (eCRF). Given the long half life of tafenoquine, the maximal pharmacodynamic effects such as potential hemolysis or methemoglobinemia may occur several days after completion of dosing. These data will be recorded, as they comprise an essential evaluation that needs to be done before discharging any subject from the study. Therefore, the investigator should continue following subjects for all protocol assessments, up to and including Day 180 whenever possible. The subject should be given appropriate rescue therapy according to local treatment guidelines if they develop a malarial recurrence (see Section 6.9.1.2).

Subjects should discontinue taking study treatment if they meet **any** of the criteria below:

- Intolerable AEs:
  - Any grade 4 AE or toxicity in the absence of compelling evidence that the AE is not related to investigational product(s)
- Clinically significant laboratory results considered by the investigator to warrant withdrawal from the study treatment
- Liver chemistry stopping criteria (refer to Section 5.4.1 and Section 12.2 Appendix 2)
- Hemoglobin stopping criteria: Given the hemolytic potential of TQ and PQ in subjects with G6PD deficiency, study specific hematologic stopping criteria will be employed (refer to Section 5.4.2)
- QTc stopping criteria (refer to Section 5.4.3)

When QT or hemolytic stopping criteria are met, this must be promptly reported by the investigator to GSK as a Serious Adverse Event (see Section 7.5)

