#### 5.4.2. Hemoglobin Stopping Criteria

Blinded study treatment will be stopped immediately in any subject who meets the protocol-defined criteria for Hb drop (See Section 7.5.1.1) AND has EITHER clinical evidence of hemolysis OR laboratory evidence of hemolysis based on an assessment of the tests listed below. These laboratory tests will be performed immediately once a protocol-defined Hb drop is noted by the investigator.

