##### Clinical Chemistry

- Creatinine
- BUN
- Total bilirubin
- Indirect bilirubin
- AST
- ALT
- Alkaline phosphatase
- CPK
- LDH
- Visual inspection of urine and dipstick

Subjects will also be required to have a repeat G6PD quantitative phenotype test to confirm that they are not G6PD deficient. G6PD genotyping may be performed if repeat phenotyping would not define G6PD status (e.g. transfusion given or high reticulocyte count).

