#### **6.9.1.2. Rescue Medication**

Subjects diagnosed with *P. vivax* relapse (i.e. a positive blood smear with or without vivax symptoms) during the 180 day follow up period will be given an ACT plus PQ 0.5mg/kg for 14 days as rescue medication. These subjects will continue to be monitored for safety and efficacy at all scheduled visits through Day 180. Details of rescue medication including reason for the rescue medication will be recorded in the eCRF. Rescue medication will be sourced locally.

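### Every Day 180 completer without recurrence and every relapser is to receive primaquine 0.5 mg/kg for 14 days, with no exception for a participant found G6PD deficient after randomisation or stopped for haemolysis

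*Protocol*

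**What the plan says.** **End of study.** Section 6.8 covers every Day 180 completer without recurrence: "All subjects who complete the Day 180 visit and have not had a recurrence of" *P. vivax*. Section 4.1 repeats it ("Subjects who have not relapsed prior to the Day 180 visit will be given open label PQ 0.5mg/kg daily for 14 days"), as do Section 4.4 ("To ensure that all subjects do receive anti-hypnozoite treatment, subjects who have not relapsed by Day 180 will be dosed with PQ") and Section 4.6.2 ("Any subject who has not relapsed by the 6 month timepoint will be treated with open label PQ for 14 days"). The synopsis, the Figure 1 notes, the risk table in 4.6.1 and the Time and Events table in 7.1 carry the same rule.

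**Relapse.** Under Section 6.9.1.2, subjects diagnosed with relapse "during the 180 day follow up period will be given an ACT plus PQ 0.5mg/kg for 14 days as rescue medication". The synopsis, Section 4.1, the Figure 1 notes and the Time and Events table repeat this.

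**Haemoglobin and G6PD.** Section 5.4.2 states: "Blinded study treatment will be stopped immediately in any subject who meets the protocol-defined criteria for Hb drop", provided there is also clinical or laboratory evidence of haemolysis. It adds: "Subjects will also be required to have a repeat G6PD quantitative phenotype test to confirm that they are not G6PD deficient". Participants who stop treatment stay in the study under Section 5.4: "Therefore, the investigator should continue following subjects for all protocol assessments, up to and including Day 180 whenever possible".

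**The concern.** The protocol expects that G6PD deficiency may come to light after randomisation and arranges testing for it. It does not say what a deficient result means for the PQ that follows. A participant with a deficient quantitative result on file, or who has already haemolysed on blinded treatment, therefore still falls under the instructions in 6.8 or 6.9.1.2. Followed as written, they give him an 8-aminoquinoline in the situation the entry criteria are meant to prevent. What is at stake is the safety of a small number of participants.

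**Working it through.** This turns mainly on reading the sections together. The only arithmetic is the dose and the timing of the last haemoglobin.

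**1. Can deficiency surface after randomisation?** Yes. Entry rests on a qualitative point-of-care test (inclusion criterion 4). The quantitative assay is not back at randomisation (4.1, 7.2) and arrives shortly after enrolment (4.4). A protocol-defined haemoglobin drop triggers another quantitative test (5.4.2, 7.5.1.1), with genotyping if phenotyping would not settle the matter. SAP 8.3.1 plans a profile plot for any participant found deficient.

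**2. What follows from such a result?** Discordant results lead to review and re-testing (4.1, 7.2). A haemoglobin drop with haemolysis stops blinded treatment (5.4.2). Neither section mentions open label or rescue PQ.

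**3. Does the participant still reach the PQ instruction?** Yes. Section 5.4 keeps him attending to Day 180. There he meets 6.8 if he has not relapsed. If he relapses, he meets 6.9.1.2.

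**4. Would another rule intervene at that point?**
- The PQ contraindications, including a history of haemolytic anaemia, are exclusion criteria (5.2, item 13). Section 4.5 refers to deficiency at screening.
- The haemoglobin-drop definition covers only the first 15 days (7.5.1.1), so it cannot operate during a course starting at Day 180.
- Scheduled haematology ends at Day 120, and relapse haematology is done only up to Day 120 (7.1). The Day 195 visit lists only concomitant medication, AEs and SAEs.
- From the last planned haemoglobin to Day 180 is 180 − 120 = 60 days. With the windows in SAP 11.3.1 (Day 120: 106 to 135; Day 180: 170 to 190) the gap runs from 170 − 135 = 35 to 190 − 106 = 84 days.

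**5. How large is the later dose?** Blinded PQ is 15 mg/day, or 15 × 14 = 210 mg in total.

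| Weight | Later daily dose | Ratio to 15 mg |
|---|---|---|
| 50 kg | 0.5 × 50 = 25 mg | 1.7 |
| 60 kg | 0.5 × 60 = 30 mg (420 mg over 14 days) | 2.0 |
| 75 kg | 0.5 × 75 = 37.5 mg | 2.5 |

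Only the 60 kg case is worked in the protocol (4.5). The other weights are illustrative.

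**6. Who is least protected?** With 1:1:1 allocation, one participant in three is on placebo. In a deficient man on placebo no blinded drug would have revealed the problem, and the later PQ would be his first 8-aminoquinoline in the trial. Section 9.2.1 assumes 50% relapse-free efficacy on DHA-PQP alone, so in that arm rescue is as likely a route to PQ as Day 180.

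**7. How many?** This cannot be estimated. The documents give neither the share who pass the spot test and prove deficient nor the share stopped for haemolysis.

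**The case against.** The strongest reply is that no clinician would give PQ to a man with a deficient result on file, and that the protocol leaves room not to.

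- Sections 4.4 and 5.4 describe rescue as following local treatment guidelines. This is real latitude, but both point to Section 6.9.1.2, which specifies PQ 0.5 mg/kg. Section 4.5 calls that dose consistent with the guidelines. What they advise in deficiency is not in the documents.
- Section 5.4 allows withdrawal for safety, and 6.8 makes the investigator responsible for considering post-study care. The introduction to Section 7 bars waivers except for immediate safety concerns. All of this permits withholding PQ; none of it says to do so.
- Section 5.4 lists the haemoglobin criteria under stopping study treatment, a wider term than the blinded treatment of 5.4.2. But the Section 6 table describes over-encapsulated 15 mg PQ, whereas the later PQ is sourced locally. Nothing says that the stop extends to it.
- Sections 2.1.4 and 4.6.1 say deficient subjects will be excluded, and 4.6.3 gives avoiding haemolysis as the reason. The intent plainly opposes PQ in known deficiency, which supports writing the exception down.
- Investigator training covers management of haemolysis (4.6.1), and the SRM covers G6PD testing (4.1, 7.2). Neither is available here and either may say more. Sections 6.8 and 6.9.1.2 do not refer to them on this point.
- The case is rare. That stands: Section 4.4 describes the spot test as highly reliable in men and intermediate values as unlikely.

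**Conclusion.** The gap is real and should be fixed. As written, Sections 6.8 and 6.9.1.2 direct PQ, at about twice the blinded dose for a 60 kg man, to participants in whom Sections 2.2 and 4.5 identify a haemolysis hazard. General safety wording lowers the risk without supplying an exception. The conclusion assumes that the instructions are followed literally and that the SRM and training materials add nothing.

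Three stronger readings are not supported:

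- **That the protocol ignores late-found deficiency, or that PQ would in practice be given.** It provides for testing, review and re-testing. Only the link to later PQ is missing.
- **That at least one case is likely.** With an assumed 2% deficient among 150 randomised, the chance of at least one is 1 − 0.98^150 = 95%; at 0.1% it is 1 − 0.999^150 = 14%. No document supplies the rate, and the spot-test description in 4.4 gives no support to the upper end.
- **That the same fault exists for liver events.** Section 5.4.1.1 already bars restarting study treatment. Whether it reaches the later PQ is not stated, so no defect can be asserted.

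**What to change.** Add to Sections 6.8 and 6.9.1.2:

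> Primaquine is withheld from any subject with a deficient quantitative G6PD result, pending repeat testing, and permanently if deficiency is confirmed (repeat quantitative test or genotype). A subject stopped under Section 5.4.2 receives primaquine only after Medical Monitor review of the repeat quantitative G6PD result and haemoglobin. Relapsing subjects still receive the ACT without delay.

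Put a cross-reference wherever the rule is repeated: the synopsis, 4.1 and the Figure 1 notes, 4.4, the 4.6.1 risk table, 4.6.2 and the Time and Events table. Name the quantitative test, because SAP 11.6.2 defines deficiency by the spot test alone, which a late-found case would typically have passed. Neither document sets a threshold for a deficient quantitative result, so the sentence should point to one.

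**Cost.** A short amendment with ethics approval (10.2), and no new visit. If the Medical Monitor wants a current haemoglobin before the Day 180 course, each stopped participant needs one extra sample, since the last planned one is at Day 120.

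**Downside.** PQ may be delayed or omitted in a very few participants, who are then managed under local guidelines. The aim in 4.4 and 4.6.2 that everyone receives anti-hypnozoite treatment would need qualifying.

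**Effect on the analysis.** The primary analysis uses the first relapse and nothing after the Day 180 visit, so it is untouched. The descriptive count of relapses per subject (SAP Table 2.29) could shift slightly if a relapser goes without rescue PQ.
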